#### 6.4.3 Study Assessments

The research assessors will not be involved in any way with the treatment and will be blind to treatment condition. There will be three primary assessment points: (i) before treatment when the infant is 4½ - 9 months, (ii) at the end of the treatment when the infant is 12 months, and (iii) at follow-up a year later when infant is 24 months. At all three time-points assessments will be made in the family home. Interactions between mother and infant, using toys that we will provide, will be filmed and coded (by coders blind to therapy arm). At 6 months, a full assessment (using the SCID) of the mother's mental state will also take place. At the second assessment visit (child 12 months old) assessment of maternal appraisal of infant facial and vocal expression task, assessment of child attachment tasks ((i)mother/child play, audio clips to child in mother's absence, reunion (ii) assessment of the mother's manner in which she conveys information about different attachment scenarios to her child) will be conducted. In addition the CBCL and language scale of the BSID-III, and the Health Care Utilisation Questionnaire will be conducted. At the third assessment visit (child 24

months) an additional assessment will take place in our research unit to assess the child's cognitive and language development (Bayley BSIDIII), attention (ECVT, Leiter, Spacial Conflict and Visual Search tasks) and emotional regulation (Rothbart Lab-TAB). In addition, the Attachment Q-Sort will be conducted and the Health Care Utilisation Questionnaire will be given to the participant. Mothers will also be asked to complete a questionnaire on their musical training and habits. Mothers who have already completed the final assessment will be sent a copy via post/email (according to their preferred method).

In addition the EPDS will be repeated during the 6th therapy session to monitor maternal mood. Finally, assessments of the partners of mothers in the study will be conducted by questionnaire, in agreement with the mother, and where the partner chooses to opt-in. EPDS and GHQ-12 will be administered at each assessment point to gauge the partner's mental state. A health history questionnaire will also be administered (Partner Additional Questions). The partner's mental state will be analysed as a covariate.

Following completion of final assessment and collection of outcome data a sub-sample of participants (n=20) will be invited to take part in a qualitative sub-study investigating participant experiences of treatment.

The project will consist of two home visits. The first session will be an unstructured interview with only one overarching question asked "Can you tell me about how you found the therapy you received from the beginning, through the different sessions to the end". This will be followed by a series of specific questions based on the issues raised by the participant. The second session will comprise of a semi-structured interview. It will be used flexibly to follow-up questions raised during the first interview which we need to explore in more detail. The visits will last between 1-2 hours. Participants will be reimbursed £20 for each visit. The interviews will be conducted by a graduate student with prior experience conducting qualitative interviews. The conversations will be audio-recorded with the consent of the participants and all procedures outlined regarding data storage and confidentiality already in place will be followed.

Participants will be identified by the Trial Coordinator.

Participants will be approached during their last assessment with the study and the researcher will ask the mother if this is something she would be interested in hearing more about or taking part. If participants have already completed the final assessments the researcher who saw them last will contact and ask if they would be interested in hearing more about this. Following this their details will be passed on to the interviewer who will call to explain more about the study and arrange a home visit if they are interested.

All SOPs currently in place will also be used for this qualitative project detailed in Section 8 of the Protocol v.10.0. Supervision and consultation will be available by a Consultant Psychiatrist (PI to the study) in the event that the participant is distressed following the interviews.

Part of this work will be used by the research assistant working on the project for her Master's dissertation for Birkbeck College, London.

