## 6.2 Primary and Secondary Endpoints/Outcome Measures

### Principal outcome variables at 24 months

1. *Child cognitive development* will be measured using the Bayley Scales of Infant Development-Third Edition (BSID-III). We will use the cognitive and language scales as the principal outcome. This is a widely used and validated measure of cognitive functioning at this age and has recently been updated.

2. *Behaviour problems* will be assessed by the Child Behaviour Checklist (CBCL) (2-3 yearold version) which is widely-used and well-validated. The principal outcome will be the externalising scale of the CBCL.

3. *Attachment security* will be measured by the Attachment Q-Sort (AQS), a 90 item q-set designed to measure the security of a child's attachment behaviour during naturalistic observations in the family home. It has been shown to be reliable with good discriminant validity. The items consist of numerous descriptors of behaviour typical of children between the ages of 12 and 48 months and these items are sorted by trained observers on the basis of extensive observations lasting for at least 1.5 hours.

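### Protocol 6.4.3 gives two incompatible times for the qualitative sub-study approach, and one of them risks unblinding an assessor before 24-month outcomes are recorded

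*Protocol*

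**What the plan says.** Protocol section 6.4.3 opens with the blinding rule: "The research assessors will not be involved in any way with the treatment and will be blind to treatment condition".

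Later in the same section the qualitative sub-study is introduced with one timing: "Following completion of final assessment and collection of outcome data a sub-sample of participants (n=20) will be invited to take part". A few paragraphs on, the practical instruction gives another: "Participants will be approached during their last assessment with the study and the researcher will ask the mother" whether she would like to hear more or take part. Mothers who have already finished are handled separately: "the researcher who saw them last will contact and ask if they would be interested in hearing more about this".

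The topic is the mother's treatment. The single overarching interview question is "Can you tell me about how you found the therapy you received from the beginning, through the different sessions to the end". The interview is not done by the assessor: "The interviews will be conducted by a graduate student with prior experience conducting qualitative interviews". The Trial Coordinator identifies the participants, and the interviewer telephones those who are interested.

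On outcomes, section 6.2 says the Attachment Q-Sort (AQS) items are "sorted by trained observers on the basis of extensive observations". Section 6.4.3 adds a research-unit assessment at 24 months, with the Bayley-III, attention tasks and Lab-TAB, to the home assessment.

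**The concern.** Mothers and therapists cannot be blind in this trial, so blind assessment is the main safeguard for the 24-month outcomes that a researcher rates or scores. The two arms differ in ways a mother would mention without thinking: being filmed and watching the clips, or muscle relaxation with recordings to practise at home (section 7). A blind assessor who asks, during the outcome visit, whether she would like to talk about her therapy gives her an occasion to say which one she had.

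If that happens before the AQS is sorted or a test is scored, the rating of a principal outcome is no longer blind for that child. Nothing in the section requires ratings to be finished before the approach, asks the mother not to disclose her treatment, or gives the approach to someone who does not rate outcomes.

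**Working it through.** **1. The two timings side by side (section 6.4.3).**
- Opening sentence: the invitation follows the final assessment and the collection of outcome data.
- Practical instruction: the approach takes place during the last assessment.
- The next sentence treats mothers who have already completed the final assessments as a separate case. For the others, then, the approach is not after completion. As written, the two statements conflict.

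**2. Who makes the approach.** The instruction names only the researcher at the last assessment, or for finished mothers the researcher who saw them last. Section 6.4.3 says research assessors are blind. That the researcher is a blind assessor is therefore an inference, but a firm one, because no other person is named for this step.

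**3. Which outcomes could still be open.**
- AQS: sorted by observers on the basis of at least 1.5 hours of home observation (section 6.2). No text says it is sorted before the approach.
- Bayley-III, attention tasks, Lab-TAB: given at a separate research-unit assessment. The order of the home and unit parts is not stated.
- CBCL externalising: maternal report (Synopsis), so assessor unblinding does not touch it.
- Filmed mother-infant interactions: coded by coders blind to arm (section 6.4.3).

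**4. Size.** The protocol states no figure to reproduce, so this is illustrative.

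Inputs:
- Analysed sample 2 x 57 = 114 (section 9.1).
- Sub-study size 20 (section 6.4.3).
- Shift in the between-arm rating difference among unblinded children: 0.3-0.5 SD (assumed).

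Formulas:
- Bias = (number unblinded before rating / 114) x shift.
- SE of the difference = sqrt(2/57) = 0.187 SD.
- Two-sided 5% false-positive rate = P(Z > 1.96 - bias/SE) + P(Z < -1.96 - bias/SE).

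| Unblinded before rating | Fraction | Bias (SD) | False-positive rate |
|---|---|---|---|
| 0 | 0 | 0 | 5.0% |
| 5 (assumed: half of 20 already finished, half of the rest disclose) | 5/114 = 0.044 | 0.013-0.022 | about 5.1-5.2% |
| 20 (assumed: all approached mid-assessment, all disclose) | 20/114 = 0.175 | 0.053-0.088 | 5.9-7.5% |

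For scale, the protocol's detectable difference with 57 per group is 0.532 SD (section 9.1).

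**The case against.** The strongest reply is that the two sentences can be read together: interest is sounded out at the close of the last visit, and participation follows once outcomes are collected. The step is also narrow. The researcher asks only about interest, the interviewer explains by telephone, and a graduate student conducts the interview. Any 24-month contact with a mother who knows her treatment carries some risk of disclosure, so only the increment counts. Bayley items are scored pass or fail and the assessments are video-recorded (section 9.2), so blind re-scoring is possible.

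Much of this stands, and it keeps the point modest. It does not remove it. The text says during the assessment, not at its close or after scores are recorded, and the AQS has no stated equivalent of video re-scoring.

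A reader might infer three stronger things that the documents do not support:
- **That at least 20 mothers are exposed.** Some of the 20 come from mothers who had already finished, and the split is not given. Nor is 20 a strict ceiling, since more may be asked if some decline, but no decline rate is given.
- **That the false-positive rate rises to 9-16%.** This needs 40 mothers approached mid-assessment (40/114 = 0.351, bias 0.105-0.175 SD), every one disclosing before rating. Nothing in the protocol supports that combination.
- **That the Trial Coordinator's choice of mothers is itself a cue to arm.** Nothing says selection depends on arm.

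**Conclusion.** The point holds as an internal contradiction with an avoidable risk to blinding. It does not show that outcomes were or will be biased. Section 6.4.3 gives two incompatible times for one step, and the more specific instruction has an evidently blind assessor raise the mother's therapy at the primary endpoint visit. The exposure is chiefly the AQS, and possibly the Bayley-III and other examiner-administered tests, depending on visit order and when scores are recorded. The CBCL is outside it.

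The size cannot be derived from the protocol, because the number approached mid-assessment, the share who disclose and the effect on ratings are all unknown. The range of near zero to about 0.05-0.09 SD rests on those assumptions. Its upper end needs 20 of 114 mothers all disclosing before rating. The case for change rests on the conflicting text and the ease of removing the risk, not on these figures.

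**What to change.** In section 6.4.3, delete the approach during the last assessment. State instead that the Trial Coordinator or the qualitative interviewer, not an outcome assessor, makes first contact, and only after all of that mother's 24-month visits are complete and her assessor-rated scores are recorded. Use the same contact person for mothers who have already finished, in place of the researcher who last saw them. This makes the practical instruction agree with the section's own opening sentence on the sub-study and with its blinding rule.

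The cost is about two sentences of text. The coordinator already identifies participants and the interviewer already telephones them, so no new staff are needed. The drawback is slightly slower recruitment to the sub-study.

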## 6.5 Definition of End of Study

The end of study is the date of the last visit of the last participant. The funding period of the study runs to 31 August 2015 and coding and analysis will continue beyond the date of the last visit.

## 7. INTERVENTIONS

The three therapies which constitute the study interventions are outlined here. All participants will receive Cognitive Behaviour Therapy (CBT). They will also be randomised to receive either Progressive Muscle Relaxation (PMR) or Video Feedback Therapy (VFT). All therapies will be delivered to each participant by the same therapist, and within the same visits (i.e. CBT and VFT/PMR at every therapy session). There will be five weekly sessions to begin with between 6-8 months , followed by five fortnightly sessions around 8-12 months, and then by two booster sessions at 16 and 20 months. At the end of session 3 the participants will be asked the extent they believe the treatments they have been allocated will help them (Expectation Questionnaire).

## Cognitive Behaviour Therapy (CBT)

The purpose of CBT is to acquire skills for managing negative thoughts and feelings. CBT for depression targets behaviours that contribute to loss of positive reinforcement from others or the environment, and cognitions that represent negative beliefs about the self, world and future.

The first stage of the therapy is aimed at lessening depression using behavioural techniques, such as daily activity schedules, pleasant event scheduling, and problem-solving. These behavioural techniques are intended to increase sources of positive reinforcement, and to replace avoidant behaviours with problem-solving behaviours. The second stage of treatment works at identifying and challenging negative automatic thoughts. Information from behavioural experimentation are used to develop and strengthen more balanced ways of thinking.

## Video Feedback Treatment (VFT)

The aim of the video-feedback treatment is to improve the quality of mother-child interaction by enhancing the three core parenting skills described previously. At most visits the therapist videotapes the mother and infant at home during general interactions and specific tasks. At the following visits, the therapist and mother watch and discuss extracts selected by the therapist to highlight the infant's signals and to draw out and enhance the mother's observational skills. The baseline assessment videotape is used in the first VFT session.

In order to help the mother with the three parenting capacities, a number of situations and tasks have been selected which enable the therapist to work with the mother on each capacity, as follows:

- Maternal focus of attention and associated contingency using book sharing and joint cognitive tasks.
- Emotional scaffolding using difficult and frustrating toys slightly above child's developmental level.
- Ability to treat the infant as a psychological agent and behavioural sensitivity to attachment cues using brief separations and exploration opportunities.

Treatment progresses by initially concentrating on the infant's perspective, focusing on his/her signals (initiatives towards the mother, exploratory behaviour, interest, and distress). In subsequent sessions this is augmented by highlighting the mother's perspective: mother-infant initiatives, mutual responses, moments of shared emotion and the success of sensitive, prompt reactions to infant cues. In the last few sessions the mother is also helped to identify and address potential triggers to specific difficulties.

## Progressive Muscle Relaxation (PMR)

The relaxation training is based on Bernstein and Borkovec's (Bernstein and Borkovec 1973) progressive muscle relaxation training and was developed to reduce tonic levels of arousal and anxiety and to be a tool for coping with stressful events. Participants are taught that cognitions and physical symptoms are connected and affect each other reciprocally, and therefore learning relaxation may lead to increased mental well-being. The programme consists of relaxation training involving progressive tensing and relaxing of 16 muscle groups, then 8, and finally just four muscle groups. Throughout, the participant is asked to concentrate on the sensations she experiences during tensing and relaxation. The next stage is relaxation-by-recall, where the participant is asked to think about what the relaxed state feels like, rather than actually tensing and relaxing muscles. The last stage of the

training consists of pairing the exhalation of a deep breath with the thought 'relax' (cuecontrolled relaxation). CDs or audiotapes containing the relaxation procedure are given to the participant and she is asked to practise at home.

More detail on all three of these therapies can be found in the Therapy Manual accompanying this protocol.

At the beginning of each session the participant will be asked to complete the PHQ-2 (2 items) to assess their mood to allow us to monitor the progress of their mental state.

## 8. SAFETY

All research staff will be required to undergo Enhanced CRB checks.

It is not anticipated that any serious adverse events will occur. Safety will be kept under review by the Trial Steering Committee and Data Monintoring and Ethics Committee and any serious adverse event will be reported to the sponsor and the REC within 15 days.

## 8.1 Staff Safety

A risk assessment on home visits will be conducted prior to the study commencing and a specific plan of action put in place for recording the researcher's whereabouts (e.g telephoning on arrival at home visit and on departure). Further detail of this 'buddy system' can be found in SOP Risk & Safety: Home Visits.

## 8.2 Child Protection

If there are significant child protection concerns we will follow the OBMH protocol, Safeguarding Children, in the event of such issues arising. The therapists will always be in close contact with the CI.

## 8.3 Safeguarding Vulnerable Adults

Working with vulnerable adults, it is important to ensure they are safeguarded. We will follow the OBMH protocol, Safeguarding Vulnerable Adults. We will ensure it is made clear to healthcare professionals, participants and research staff that clinical responsibility lies with the healthcare professional whose care the participant falls under (usually the GP).

## 9. STATISTICS AND ANALYSIS

## 9.1 Number of Participants

The target number of participants is 144 (72 in each arm). The sample size calculation is based on the Bayley Mental Development (MDI) Index using the Bayley second edition. Cornish and colleagues (2008) report summaries of the Bayley MDI scale in 15-month-old children according to PND in mothers – no history, brief PND and chronic PND. Based on a standard deviation of 10.9, as reported for those children with mothers suffering chronic PND, a sample size of 57 per group is necessary to detect a difference of 5.8 (as found by Cornish) in the Bayley MDI scale, at the 5% significance level with 80% power. Allowing for 20% loss to follow-up, a conservative estimate given the low attrition in our trials to date ([name] et al 2006, Cooper et al 2003), 72 participants per group are required.

This study uses the Bayley Scales of Infant Development III to measure the main outcome. It gives a score for cognitive and language development. The previous version of this measure provided with an aggregate score of cognitive, language and fine motor development known as the Mental Development Index. The Third edition of this measure does not provide an aggregate score; the sub scales (cognitive and language development) are used separately. Our original sample size calculation was based on published data using the Bayley (version II). With respect to the cognitive and language subscales available in the Bayley (version III), the proposed sample size will have 80% power to detect a difference of 0.532 standard deviations between the randomised groups.

Piteo and colleagues (2012) report Bayley III cognitive and language subscale scores at 18 months in 69 children of mothers with maternal depression in the first six months postpartum. The standard deviations for cognitive and language subscales were 11.9 and 13.5 respectively. Assuming similar levels of variability are seen in this trial, our proposed sample size of 57 per group will have 80% power to detect a minimum difference of 6.3 in the cognitive scale and 7.2 in the language scale of Bayley III.

#### 9.2 Analysis

With regard to child behaviour problems, a sample size of 57 allows for differences between groups of 0.532 standard deviations to be detected at the 5% significance level and 80% power. Trapolini and colleagues (2007) report Child Behaviour CheckList (CBCL) maternal ratings of externalising behaviour in 4-year-olds. These were grouped according to mothers' depression, as never, sometimes and chronic. The standard deviation of the mothers' scores in the chronic depression group was 7.70, which would allow a difference of 4.08 to be detected if similar variability was observed in this trial. The means and standard deviations in our current Trust programme on the 65% of the sample analysed so far, for 2-year-old children of mothers who remain depressed at 6 months, are very similar to those of Trapolini.

For attachment, van Doesum and colleagues (2008) report Attachment Q-Sort (AQS) security in children 18 months of age, with a common standard deviation of 0.326, which would allow for a difference of 0.17 to be detected if similar variability was observed in this trial.

It is hypothesised that, compared to the control treatment, VFT will lead to better cognitive development, fewer behaviour problems, and a higher rate of secure attachment (Hypothesis 1). To test Hypothesis 1 ANOVAs will be conducted (with each of the child outcomes measured at 24 months as the dependent variable and the treatment group as a betweengroup factor). The three secondary outcome variables will be analysed similarly. Hypothesis 2 has three components: (i) to examine whether, compared to the control group, VFT leads to greater improvement in the three parenting capacities, ANCOVAs (co-varying for the 6m baseline measure) will be performed on each capacity; (ii) to test for mediation, initially the role of single mediators will be examined using standard regression analysis (including any relevant covariates) (Kraemer, et al, 2002); (iii) to establish the unique contribution of each mediator (since the potential mediators might be associated), exploratory mediational analysis using bootstrapping techniques will be conducted (in line with Preacher et al 2007), that include the two non-targetted maternal capacities as covariates. Given the increased complexity of the models including covariates, and our sample size, bootstrapping techniques will be used to also provide confidence intervals (after MacKinnon & Fairchild, 2009).

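### The 24-month-only ANOVA for CBCL externalising and BSID-III language leaves scheduled 12-month scores unused, so loss after 12 months that differs by arm can bias the comparison

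*Protocol*

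**What the plan says.** Section 9.2 of the protocol names the test for the primary hypothesis: one ANOVA per child outcome, "with each of the child outcomes measured at 24 months as the dependent variable and the treatment group as a betweengroup factor". No other term is named for that test. The same paragraph adjusts for the 6-month baseline when it compares the parenting capacities.

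Section 6.4.3 lists what is measured at 12 months: "In addition the CBCL and language scale of the BSID-III, and the Health Care Utilisation Questionnaire will be conducted". At 24 months, "an additional assessment will take place in our research unit to assess the child's cognitive and language development (Bayley BSIDIII" and other tests; the section then continues: "In addition, the Attachment Q-Sort will be conducted and the Health Care Utilisation Questionnaire will be given to the participant". So CBCL and BSID-III language are scheduled at both visits. The BSID-III cognitive scale and the Attachment Q-Sort (AQS) are listed only at 24 months.

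Section 9.1 provides for missing outcomes: "Allowing for 20% loss to follow-up, a conservative estimate given the low attrition in our trials to date", which takes 57 analysed per arm up to 72 recruited. It does not say how much of the loss is expected before 12 months and how much after.

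**The concern.** A child with no 24-month score cannot enter a 24-month ANOVA, so the method as stated is in effect a complete-case comparison. For CBCL and BSID-III language, a family that attends at 12 months and is then lost has already supplied a score on the same instrument, and the stated test gives that score no role.

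This matters if loss is selective in a way that differs by arm. One arm works on the mother's interaction with her child and the other on her own relaxation. Section 6.4.3 describes assessors and coders as blind, while participants know which therapy they receive. The 24-month assessment also adds a visit to the research unit. It is plausible, though nothing in the protocol shows it, that how the child is doing affects retention more in one arm than in the other. The children seen at 24 months would then differ between arms for reasons other than treatment, and the 12-month score carries information about that selection.

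**Working it through.** **1. The plan's own figures.** Inputs from section 9.1: "Based on a standard deviation of 10.9"; "a sample size of 57 per group is necessary to detect a difference of 5.8"; "at the 5% significance level with 80% power". Two-sided testing is assumed, since sidedness is not stated.

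- Normal approximation: n = 2 × (1.960 + 0.842)² × 10.9² / 5.8² = 55.4, so 56 per group. With the noncentral t, power is 79.7% at 56 and 80.4% at 57, so 57 is reproduced.
- Loss: 57 / 0.80 = 71.25, so 72 per group. In reverse, 72 × 0.80 = 57.6, so about 57 or 58 per arm would enter the ANOVA.
- Detectable difference: 5.8 / 10.9 = 0.532 SD, as stated (0.529 SD by the t calculation). The protocol gives 4.08 points for CBCL externalising (SD 7.70) and 7.2 for language (SD 13.5).

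The sample size is sound, and it shows that the plan expects roughly 14 or 15 families per arm without a 24-month score.

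**2. Size of a possible bias.** The protocol gives no correlation, no dropout mechanism and no timing of loss, so these are assumptions:

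- no true treatment effect, and 20% lost in each arm, all after 12 months;
- in one arm loss is unrelated to the 12-month score; in the other the log-odds of loss change by 0.5 or 1.0 per SD of that score (odds ratio 1.6 or 2.7);
- 12-to-24-month correlation r of 0.4 or 0.6.

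With scores in SD units, bias = r × (shift in the mean 12-month score among those retained). At 20% loss that shift is 0.096 SD for slope 0.5 and 0.173 SD for slope 1.0.

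| Slope | r | Bias (SD) | CBCL points (× 7.7) | Language points (× 13.5) |
|---|---|---|---|---|
| 0.5 | 0.4 | 0.038 | 0.30 | 0.52 |
| 0.5 | 0.6 | 0.058 | 0.44 | 0.78 |
| 1.0 | 0.4 | 0.069 | 0.53 | 0.94 |
| 1.0 | 0.6 | 0.104 | 0.80 | 1.40 |

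Large-sample simulation agrees (0.038, 0.057, 0.069 and 0.103 SD).

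**3. Other assumptions.**

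- Same selection in both arms: the shifts cancel and the bias is about 0 (simulated values within 0.002 SD of zero).
- Opposite selection in the two arms: the shifts add, giving 0.08 to 0.21 SD over the same slopes and correlations.
- Half of the loss before 12 months and random: 10% is lost early and 0.10 / 0.90 = 11.1% of the remainder late. The shift becomes 0.054 or 0.100 SD, and the one-arm bias 0.02 to 0.06 SD.

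**4. Effect on the test.** The standard error of the difference at 57 per arm is √(2/57) = 0.187 SD. A bias of 0.04 SD is 0.2 standard errors and moves the two-sided 5% error to about 5.5%. A bias of 0.10 SD is 0.5 standard errors and moves it to about 8%.

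**5. What the 12-month score recovers.** When the 24-month means were estimated with the 12-month score of every child who had one, the simulated bias fell to about zero in every scenario. That follows from the set-up, because simulated loss depended only on that score. The variance of each 24-month mean falls by a factor of about 1 − 0.2r², which is 3% at r = 0.4 and 7% at r = 0.6.

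**The case against.** The strongest objection is that missing-data handling belongs in a statistical analysis plan, which is not shown. The protocol nowhere says that families lost after 12 months are discarded, and a 24-month comparison can be combined with imputation. This stands to the extent that silence on missing data is no fault here. It does not remove the point, because section 9.2 names the model, its dependent variable and its only factor, and that model has no place for the 12-month scores.

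A reader might infer that the primary comparison **is** biased. The documents do not support that. Outcome-related loss alone is not enough; it must differ between the arms, and nothing in the protocol shows that it will. Both arms receive CBT from the same therapist in the same visits, and assessment visits are paid in both arms.

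A reader might also infer that existing data would repair every primary score. They would not. The cognitive scale and the AQS have no listed 12-month counterpart, and section 6.4.3 does not say which CBCL version is used at 12 months, whereas section 6.2 names the 2-3 year-old version for the outcome.

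Timing is a fair criticism too. The main therapy ends at about 12 months, so loss driven by therapy content may come earlier, before any 12-month score exists. The sizes above are upper figures in that respect.

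**Conclusion.** The point holds for CBCL externalising and BSID-III language. The stated test ignores scheduled 12-month scores, which leaves it open to bias from loss after 12 months that differs by arm. Under one-arm selection, all 20% lost after 12 months and a correlation of 0.4 to 0.6, the bias is about 0.04 to 0.10 SD, or 7% to 19% of the detectable 0.532 SD. It is about zero with equal selection, smaller if much of the loss is early, and larger (to about 0.21 SD) if selection runs in opposite directions. None of these inputs is in the protocol, so the figures show what could happen and are not a forecast. The likely harm is modest. The change should be made because it is cheap and uses data that the trial already schedules.

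**What to change.** In section 9.2, for CBCL externalising and BSID-III language, make the primary analysis a likelihood-based repeated-measures model:

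- include the 12- and 24-month scores of every randomised family with either score, analysed as randomised;
- fit separate means for each arm at each time and an unstructured covariance, so the two CBCL scores need not come from an identical version;
- report the 24-month contrast between arms;
- keep the 24-month ANOVA as a sensitivity analysis.

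If no scores are missing, this model gives the same 24-month difference as the ANOVA.

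For BSID-III cognitive and the AQS, keep the 24-month analysis. There the 12-month scores are at most auxiliary variables in a sensitivity imputation. Few predictors should be used, since only about 57 children per arm would be observed.

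The cost is a few sentences and modest analysis work, with no new data. The model relies on data being missing at random given the 12-month score, and it does nothing for families lost before 12 months. The write-up should therefore report loss by arm before and after that visit. The CBCL version used at 12 months should also be stated.
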